5.2.2. Estimand

The difference in the RSV RNA log₁₀ viral load AUC_{1-7Days} for active versus placebo treatment will be derived from the mixed model specified in section 5.2.3, deriving least square mean differences, including the nominal 95% 2-sided confidence intervals in the Intention-To-Treat-infected (ITT-i) set.

These estimates are customary and will not be used to conclude for a positive dose-response relationship, but are relevant for reviewers to understand the effect of each dose on the viral load and the customary level of uncertainty associated with it.

5.2.3. Analysis Methods

Mean \log_{10} viral load values over time will be analyzed using a restricted maximum likelihood based repeated measures approach. Analyses will include the fixed, categorical effects of treatment, stratification factors, analysis visit, and treatment-by-analysis visit interaction, as well as the continuous, fixed covariates of baseline \log_{10} viral load and baseline \log_{10} viral load by-analysis visit interaction. An unstructured covariance structure will be selected. In case this model will not converge, the following list of covariance structures will be applied and a selection will be based on the Akaike Information Criterion for those that do converge:

- Unstructured [UN]
- Ante-dependence [ANTE(1)]
- Heterogenous Toeplitz [TOEPH]
- Heterogeneous CS [CSH]
- Heterogeneous AR(1) [ARH(1)]
- Toeplitz [TOEP]

The Kenward-Roger approximation will be used to estimate denominator degrees of freedom. The testing of the dose-response relation is based on the expectation that higher dose regimens will be at least as efficacious as lower dose regimens with respect to efficacy on the viral load over time. Therefore, two contrasts on the dose regimens have been selected that are consistent with this expectation:

- a contrast with no difference between the 2 active regimens tested against placebo and
- a contrast with a positive linear dose-response relationship with respect to active regimens.

A multiple comparison approach will be taken testing the 2 contrasts combined versus placebo, adjusted for multiplicity.

The SAS mock code used to test the primary hypotheses will be as follows:

```
proc mixed data=viral_load;
  where avisitn in (2,3,4,5,6,7)
  class avisitn trt usubjid stratum;
  model logtiter = trt|avisitn stratum base|avisitn /ddfm=kr s;
  repeated avisitn/subject=usubjid type=un;
  lsestimate trt*avisitn
  "Plateau" -4 2 2 -4 2 2 -4 2 2 -4 2 2 -4 2 2 -2 1 1,
  "Linear" -4 0 4 -4 0 4 -4 0 4 -4 0 4 -4 0 4 -2 0 2
  /divisor=4 adjust=simulate seed=3369 alpha= $\alpha$ * lower cl;
run;
```

The variable *trt* denotes the *placebo*, *low dose regimen*, and *high dose regimen* treatment groups, the *avisitn* variable denotes the swabbing visits at Days 2 through 7, and the *base* variable is the baseline \log_{10} viral load measured at Day 1.

The *lower* option is selected as the contrast needs to have a value below zero (ie, there needs to be a reduction in $AUC_{1-7\text{Days}}$ comparing active treatment to placebo). In summary, a positive dose-response relationship will be concluded if based on this analysis for any of the two estimations the resulting adjusted p-value is lower than the associated Pocock critical value (see section 5.1.1).

The differences in the $AUC_{1-7\text{Days}}$ for active versus placebo will be derived using appropriate contrasts deriving least square mean differences, including the 95% 2-sided confidence intervals.

The individual $AUC_{0-144\text{h}}$ as calculated using the trapezoidal rule will be considered as a supportive analysis and will be analyzed using a linear model with $AUC_{0-144\text{h}}$ as a dependent variable and treatment group and stratum as fixed factors, and baseline \log_{10} viral load as fixed covariate. For this analysis no adjustments for multiplicity will be applied, that is the differences versus placebo will be estimated using appropriate contrasts with 95% confidence intervals.

Before unblinding, the viral load data will be evaluated to assess whether viral load measurements based on swabs performed by the Health Care Provider (HCP) are similar as the swabs not performed by a HCP. Individual line plots will be created to visually check individual patterns for any difference between the samples. Depending on the visual inspection a decision will be made if all samples or only the samples from swabs performed by a HCP will be considered for the primary analysis. For example, if for the majority of subjects there is a clear drop in viral load when switched from samples taken by a HCP and samples taken by a non-HCP, the decision could be that only samples from swabs done by a HCP will be used. This blinded data review will be done before the database lock of the interim analysis and may also take other data sources into account.

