- Subjects will be dosed with MDs twice daily (minimum 8 hours and maximum 16 hours apart with no more than 2 doses per calendar day). Lumicitabine may be given without regard to food.
- An electronic device will be provided to the parent(s)/caregiver(s) the investigator/study-site personnel will provide sufficient information to enable the parent(s)/caregiver(s) to complete the parent(s)/caregiver(s) eCOA. Parent(s)/caregiver(s) will complete the eCOA twice daily (in the morning and in the evening) until the Day 14 visit, and once daily (in the evening) up to the Day 28 visit, at approximately the same time each day. Whenever possible, the same parent(s)/caregiver(s) should complete the eCOA throughout the study.
- Clinical evaluation includes, but is not limited to, RSV disease symptoms, vital signs, oxygen requirement (type and duration), level of hospital care, duration of hospitalization, respiratory rate, body temperature, and SpO₂.
- A complete physical examination includes all body systems.
- A directed physical examination includes respiratory system, nose, ear, throat, facial and neck lymph nodes, and skin examination.
- A 12-lead ECG is strongly preferred but in cases where a 12-lead ECG is not possible or feasible, then a 6-lead ECG may be performed.
- Leftover blood samples and nasal swabs may be used for exploratory biomarker analyses.
- Mid-turbinate nasal swabs (from the same nostril throughout the study) to assess RSV viral load and resistance should be taken by parent(s)/caregiver(s) from Day 3 to Day 6 and by a trained study team member on Day 7, Day 10, Day 14, and Day 28. Samples should be taken once daily at approximately the same time

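### Whether caregiver swabs enter the primary analysis is decided by a visual check with no threshold, whose example criterion natural viral decline at discharge can meet

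*SAP*

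**What the plan says.** SAP 5.2.3 provides for a review, before unblinding, of whether swabs taken by a health care provider (HCP) and swabs taken by others behave alike. Individual line plots are inspected, and "Depending on the visual inspection a decision will be made if all samples or only the samples from swabs performed by a HCP" are used for the primary analysis. The guidance is one example: "if for the majority of subjects there is a clear drop in viral load when switched from samples taken by a HCP" to those of a non-HCP, "the decision could be that only samples from swabs done by a HCP will be used". On timing, "This blinded data review will be done before the database lock of the interim analysis and may also take other data sources into account".

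The swab footnote of the Protocol's Time and Events Schedule after hospital discharge says that swabs "should be taken by parent(s)/caregiver(s) from Day 3 to Day 6 and by a trained study team member on Day 7". Discharge is allowed once Day 2 procedures are complete. Home swabs are refrigerated and brought to the next visit (Protocol 9.1.3). In-hospital samples are to be frozen as soon as possible (footnote to the hospitalization schedule).

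SAP 5.2.1 sets no restriction by collector: each post-baseline visit uses the swab performed that day. Missing swabs are not imputed, and the mixed model relies on missing at random.

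**The concern.** The change of collector happens at discharge. It therefore coincides with a later study day, with clinical recovery and with a change of storage. A fall within a child at that moment may mean poorer home sampling or simply a child clearing the virus, and the example criterion does not say how to tell them apart. It sets no size for a clear drop and asks for no comparison with children still swabbed by staff on the same study day.

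If the check wrongly led to HCP-only data, Days 3 to 6 would be missing because the child had gone home. Protocol 3.2 says treatment may reduce days of hospitalization, and length of stay is a secondary endpoint. Missingness in the primary endpoint would then follow an outcome that treatment may change. The primary model contains treatment, strata, visit and baseline viral load but no measure of recovery, so missing at random becomes hard to defend. Blinding stops anyone choosing by arm. It does not stop a wrong reading of the pooled plots. The SAP names no sensitivity analysis on the data set that is not chosen.

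**Working it through.** **1. AUC weight at stake.** The model in SAP 5.2.3 uses "where avisitn in (2,3,4,5,6,7"). After its opening minus sign, the plateau contrast reads "4 2 2 -4 2 2 -4 2 2 -4 2 2 -4 2 2 -2 1 1", with divisor 4. Dividing the placebo coefficients by 4 gives visit weights of 1, 1, 1, 1, 1 and 0.5 for Days 2 to 7, total 5.5. The weight on caregiver swabs depends on when the child leaves:

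| Last staff swab before discharge | Home days | Share of post-baseline weight |
|---|---|---|
| Day 2 | 3-6 | 4/5.5 = 72.7% |
| Day 3 | 4-6 | 3/5.5 = 54.5% |
| Day 4 | 5-6 | 2/5.5 = 36.4% |
| Day 5 | 6 | 1/5.5 = 18.2% |

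Counting baseline at weight 0.5 (total 6), the maximum is 4/6 = 66.7%.

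**2. Can natural decline meet the example?** The documents give no decline rate and no swab-to-swab SD. Assume a decline *d* of 0.3 to 0.7 log10 per day and a swab SD *s* of 0.5 to 1.0 log10, with equally good home swabs. The chance that a one-day drop exceeds *c* is Φ((d − c)/(s√2)).

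- Any drop (c = 0): from Φ(0.3/1.414) = 0.58 to Φ(0.7/0.707) = 0.84.
- More than 0.5 log10: from Φ(−0.2/0.707) = 0.39 to Φ(0.2/0.707) = 0.61.
- More than 1.0 log10: from Φ(−0.7/0.707) = 0.16 to Φ(−0.3/1.414) = 0.42.

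A majority drops by more than *c* only when *d* exceeds *c*. Widening *d* to 0.1-1.0 gives 53-92%, 29-76% and 10-50% for the three cutoffs.

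**3. The plan's power.** Inputs from SAP 1.4: reductions of 30% (onset ≤3 days, 40% of subjects) and 20% (the rest) on high dose, so 0.4 × 30 + 0.6 × 20 = 24%; low dose 0.8 × 24 = 19.2%; SD 34%; 60 per arm; one-sided 2.5%; Pocock-type spending over three looks. Simulating the larger of the plateau and linear statistics, with looks assumed at 1/2, 2/3 and 1 of the information, gives 96.7% (96.6% with looks at 1/3, 2/3 and 1). The plan states about 97%. Cumulative power at 120 subjects is 85-86%, against at least 80% stated. Both figures reproduce.

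**4. Precision lost under HCP-only.** Let *q* be the share discharged right after Day 2, which the documents do not give. Days 2 and 7 remain observed for everyone. Assume AR(1) correlation ρ between days and that missing at random holds. The generalised least squares variance of the weighted AUC, relative to complete data, is 1 + f × q/(1 − q). Here *f* is the part of the AUC variance not predictable from Days 2 and 7: 0.429 at ρ = 0.6 and 0.081 at ρ = 0.9. For example, q = 0.5 and ρ = 0.6 gives 1 + 0.429 × 1 = 1.429. Power is recomputed as in step 3 with the SD multiplied by the square root of the ratio.

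| q | Variance ratio (ρ 0.6 to 0.9) | Power |
|---|---|---|
| 25% | 1.14 to 1.03 | 94% to 96% |
| 50% | 1.43 to 1.08 | 88% to 95% |
| 75% | 2.29 to 1.24 | 69% to 92% |

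These figures cover precision only. Any bias from discharge-dependent missingness is additional and cannot be sized from the documents.

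**The case against.** The SAP gives an illustration, not a binding trigger: the drop must be clear, and HCP-only is then only a possibility. The review is blinded, precedes the interim database lock and may use other data. This stands, and it rules out the reading that natural decline is bound to trigger HCP-only. Only if every fall counts as clear does any positive decline give a majority. At a cutoff of 1.0 log10, the assumed rates of 0.3 to 0.7 per day never do.

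A reader might also infer that the plots cannot separate poor sampling from clearance. That goes too far. Staff take the swab again on Day 7, so poor home swabs should show a rebound there and continued clearance should not. The SAP's example, however, looks only at the switch to home swabs and never asks for the Day 7 comparison.

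Nor would the analysis rest on inpatients alone. The mixed model keeps each discharged child's baseline, Day 2 and staff-taken Day 7 values and carries them into Days 3 to 6 through the covariance.

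Finally, the check has a legitimate purpose. If home swabs read low, which refrigerated storage makes conceivable, and treatment speeds discharge, the active arms contribute more low readings. An all-swab analysis would then lean toward efficacy. That error would not be equal between arms, so some guard is needed.

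**Conclusion.** The concern holds as a flaw in a stated rule. The choice of primary data set has no threshold, and its one worked criterion does not separate who took the swab from discharge, recovery and study day. Natural decline can meet it. Whether it would depends on the meaning of clear and on a decline rate the documents do not give.

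The 73% is the maximum for one child discharged right after Day 2. It should not be read as a loss across the trial, and the contrast weights themselves do not change. With 25% to 50% of children home after Day 2, the loss of power is modest to moderate: from about 97% to between 88% and 96%, given AR(1) correlation of 0.6 to 0.9 and missing at random. The more serious exposure is that missing at random would have to hold given discharge, which is a post-randomisation outcome. The plan should be changed before the blinded review takes place.

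**What to change.** In SAP 5.2.3, replace the visual decision with a blinded pooled model of the collector effect, with a numeric threshold in log10 copies/mL fixed before the review. The model should:

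- compare home and HCP swabs on the same study day, adjusted for baseline viral load and stratum;
- use the return to staff swabs on Day 7, where a rebound points to poor home sampling and continued decline does not. This within-child comparison matters because children at home and in hospital on the same day differ in recovery.

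Keep all swabs as the default, in line with SAP 5.2.1, unless the threshold is crossed, and cross-refer the two sections. Always report the unchosen data set as a named sensitivity analysis. Line plots can stay as description.

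The cost is SAP wording, one blinded model and one extra run of the primary analysis. The remaining risk is the bias toward efficacy described above, if home swabs read low and treatment speeds discharge. The rule and the HCP-only sensitivity analysis are there to detect it.

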5.3. Secondary Endpoints

5.3.1. Definitions

Formulae to be used for derived variables, including data conversions, are provided in the tables below. Note that for time-to event variables the actual date times will be used.

5.3.1.1. RSV RNA \log_{10} viral load (qRT-PCR)

Table 1: Calculations and Conversion Formulae

Measurement	Formula
\log_{10} viral load actual values	\log_{10} of the actual values as measured with qRT PCR
\log_{10} viral load	Change = \log_{10} viral load actual value – \log_{10} baseline value

change from baseline	
Peak viral load	Highest value of \log_{10} viral load at or after the baseline measurement. The first record in time with this highest value is selected. This can be the baseline record or an unscheduled record.
Rate of decline of viral load over the first 24 hours	Calculated as a log decline/24 hours defined as: (24-hour log viral load after first dose of study drug – log viral load at baseline) / (date/time of 24-hour viral load sample – date/time of baseline viral load) Note, the 24-hour viral load may not have been measured at exactly 24 hours following first dose, but the actual date/time associated with the 24-hour viral load will be used in computing the viral load slope. In case the 24 hour measurement is not available the slope will be calculated using the Day 3 assessment (48 hours), using the same definition. If there is no measurement in that time frame, the slope will not be calculated.
RSV viral load AUC_{0-240h} RSV viral load AUC_{0-336h} [trapezoidal method]	Idem as RSV viral load AUC_{0-144h} from 0 hours until 144 hours using the trapezoid method (sensitivity analysis), but from 0 hours until 240 hours and 336 hours respectively.
RSV viral load AUC_{0-xxh} [trapezoidal method]	Idem as RSV viral load AUC_{0-144h} using the trapezoid method, but from 0 hours until xx hours, where xx will be calculated as 24 times the number of days with treatment + 1 day.
Time to peak viral load (hours) [Time-to event]	The time from initiation of study treatment until the first time point with the peak viral load (= event). Subjects for which the peak was reached at the baseline measurement will have time 0. Subjects for whom the peak is reached at the last observed time point will be censored at that time point. Subjects for which this last assessment is the baseline assessment will be censored at time 0. (Date and time of event or censoring - date and time of first dose of study drug)/3600, rounded to one decimal.

Viral load status at each time point (categorical)	
Each RSV viral load measurement will be assigned to one of the 3 categories below:
 
 Undetectable (<LOD) Detectable (<LOQ) Quantifiable (\geq LOQ)
Viral load status at each time point (binary)	
Each RSV viral load measurement will be assigned to one of the 2 categories to identify if it is undetectable. Categories will be Yes (1) or No (0).

Time to virus undetectable (hours) [Time-to event]	
The time in hours from initiation of study treatment until the first post baseline time point at which the virus is undetectable in an assessment and after which time no detectable virus assessment follows (= event).
 
For each subject in the ITT-i it will be assumed that the subject is detectable or quantifiable at baseline (even if the value is negative).
 
Subjects will be (right-) censored at the last time observation of a detectable viral load. Subjects for which this last assessment is the baseline assessment will be censored at time 0.
 
(Date and time of event or censoring - date and time of first dose of study drug)/3600, rounded to one decimal.

Time to virus undetectable (hours) [interval censored]	
The time in hours from initiation of study treatment until the first post baseline time point at which the virus is undetectable, using interval censoring.
 
The boundaries of the censoring intervals are defined as the number of hours from the start of treatment.
 
The left boundary of the interval is the last positive assessment before the first confirmed negative sample which is not followed by a confirmed positive sample (at baseline every subject is considered positive). If no negative samples are observed, the left boundary will be the last sample obtained.
 
The right boundary of the interval is the first confirmed negative sample which is not followed by a confirmed positive sample. If this is not observed, the interval is right censored.
 
A confirmed positive sample is defined as two consecutive non-negative samples; a confirmed negative sample is defined as two consecutive negative samples.
 
Last obtained sample, whether positive or negative, is always

	considered confirmed.
--	-----------------------

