2.1.2. Endpoints

Primary Endpoint

The primary endpoint is RSV viral load (measured by qRT-PCR in the mid-turbinate nasal swab specimens) AUC from immediately prior to first dose of study drug (baseline) until Day 7.

Secondary Endpoints

The secondary endpoints are:

- Safety/tolerability including AEs, physical examinations, vital signs/peripheral capillary oxygen saturation (SpO₂), ECGs, and clinical laboratory results.
- PK parameters of JNJ-63549109.
- RSV clinical course endpoints:
 - Length of hospital stay from admission to discharge and to readiness for discharge and from study treatment initiation to discharge and to readiness for discharge, with readiness for discharge evaluated by the investigator.
 - Requirement for and duration of intensive care unit (ICU) stay.
 - Requirement for and duration of oxygen supplementation/noninvasive mechanical ventilation support (eg, nasal cannula, face mask, continuous positive airway pressure) and/or invasive mechanical ventilation support (eg, endotracheal-mechanical ventilation or mechanical ventilation via tracheostomy) above pre-RSV infection status.
 - Time to no longer requiring supplemental oxygen above pre-RSV infection status.
 - Time to clinical stability defined as the time from initiation of study treatment until the time at which the following criteria are met: return to pre-RSV infection status (hereafter referred to as “normalization”) of blood oxygen level (ie, without additional requirement of supplemental oxygen compared with pre-RSV infection status), normalization of oral feeding, normalization of respiratory rate, and normalization of heart rate.
 - Time from initiation of study treatment until SpO₂ ≥93% on room air among subjects who were not on supplemental oxygen prior to the onset of respiratory symptoms.
 - Time to respiratory rate, SpO₂, and body temperature return to pre-RSV infection status.
 - Incidence of acute otitis media (defined by the investigator).
- The duration and severity of signs and symptoms of RSV infection as assessed by the PRESORS questionnaire completed by the clinician in the eCOA device.
- RSV viral load as measured by qRT-PCR in the mid-turbinate nasal swab specimens, which will be used to determine the following:
 - RSV viral load over time.

- Peak viral load, time to peak viral load, rate of decline of viral load, and time to RSV RNA being undetectable.
- Proportion of subjects with undetectable RSV viral load at each timepoint.

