5.2. Primary Efficacy Endpoint(s)

5.2.1. Definition

RSV RNA will be measured in mid-turbinate nasal swab specimens using an RSV-A/B qRT-PCR developed by DDL Diagnostic Laboratory.

The primary endpoint is RSV RNA \log_{10} viral load (measured by qRT-PCR in the mid-turbinate nasal swab specimens) area under the concentration-time curve (AUC) from immediately prior to first dose of study drug (baseline) until Day 7.

The primary estimates of the $AUC_{1-7 \text{ Days}}$ will be derived from a mixed model (see section 5.2.3 for the detailed specification). No imputations of missing data from nasal swabs post-baseline will be done in this model, as this mixed model would allow to make inferences under the missing at random assumption.

Note that for the primary endpoint the following rules apply:

- Only values as provided by the central lab will be used.
- Baseline is defined as the last measurement before first intake. In case a result is available that is no later than 1 hour after treatment initiation this may be used but only if no pre-treatment observation is available.
- For all post-baseline analysis visits the RSV RNA log₁₀ viral load result of the swab that was performed at that day will be used.
- In case multiple nasal swabs were taken on a single day the maximum on the log scale will be used as the value for that subject.

As a sensitivity analysis, descriptive statistics will be provided for the viral load AUC between 0h and 144h (AUC_{0-144h}); calculated by the trapezoidal summation rule, based on date time of sampling, including the timepoints with (imputed) values available:

$$AUC_{0-144h} = \frac{1}{2} \sum_{i=1}^n (y_i + y_{i-1}) \times (t_i - t_{i-1})$$

where $i=1,2,3,\dots,n$ are the time points when post baseline samples are collected, y_i is the log 10 viral load at the time and t_i is the time in hours post baseline. y_0 is the (imputed) log 10 viral load at baseline, t_0 is time 0 and t_n is time 144h.

The following additional rules, on top of the rules of the primary analysis, will be applied to deal with missing values before calculating the Viral load AUC_{0-144h}:

- The value at time point 0h, if not exactly at 0h, will be calculated based on intrapolation between the last observed pre-dose value and the first observed post-dose value.
- The value at 144h, if not exactly at 144h, will be calculated based on intrapolation between the last observed value before 144h and the first observed value after 144h.

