In the statistical models following predictive covariates and or baseline indicators may be included: baseline \log_{10} viral load, smoking in the environment (yes/no), presence/absence of comorbid diseases, presence/absence of comorbid diseases associated with risk for lower respiratory tract disease, presence/absence of other conditions/therapy of potential interest, days since symptom initiation, RSV subtype, use of corticosteroids, supplemental oxygen at baseline, absence/presence of other viral or bacterial infections and age as continuous variable.

Stepwise forward selection will be used to identify the prognostic factors in combination with backward elimination. A significance value of 0.05 is required for a variable to enter the model and a significance value of 0.10 is required to stay in the model.

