5.3.2.1. RSV RNA \log_{10} viral load qRT-PCR

Log₁₀ Viral Load

Descriptive statistics and mean (SE) graphs will be shown of the \log_{10} viral load actual values and changes from baseline. For exploratory purpose the \log_{10} viral load actual values and changes from baseline will also be shown by sampling method (measured in the mid-turbinate nasal swabs and endotracheal samples from intubated subjects).

Differences on RSV RNA \log_{10} viral load by qRT PCR between treatment groups and by analysis visit will be determined by using appropriate contrasts in the mixed model in which the primary endpoint is modelled. Nominal 95% confidence intervals will be used.

Peak viral load; Rate of decline

The Rate of decline of viral load over the first 24 hours will be analyzed using descriptive statistics including the geometric mean and the coefficient of variation (CV).

The log peak viral load and rate of decline of RSV RNA viral load will be compared for active groups versus placebo groups using a general linear model with treatment and strata included as fixed effects.

Residuals of the final model will be plotted in a normal probability plot.

In case the model does not fit the log peak value data well, the log transformation (ie. the log of log peak viral load) will be considered as dependent variable. The data from the model will be reported as (adjusted) differences in least squares (LS) means (in the case of untransformed data) or (adjusted) geometric mean ratios (in case of log-transformed data) of active dose groups versus placebo, including 95% confidence intervals using appropriate contrasts.

RSV viral load AUC's.

The same model used for the primary analysis will be used to test for a dose response relationship on the viral load AUC until Day 10, until Day 14 and until 1 day after last dose for subjects with treatment extension (if applicable) (respectively $AUC_{1-10Days}$, $AUC_{1-14Days}$ and $AUC_{1-xxDays}$). No corrections for multiplicity will be made, thus the significance level of alpha (α^*) will be kept at 0.05. The differences in these AUCs for active versus placebo will be derived using appropriate contrasts deriving least square mean differences, including the 95% 2 sided confidence intervals.

The sensitivity analysis will be similar as for the primary endpoint, using the calculated viral load AUCs per subject based on the trapezoidal method (AUC_{0-240h} , AUC_{0-336h} and AUC_{0-xxh}) as indicated in section 5.3.1.1.

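### Peak viral load may be the pre-dose baseline swab, so comparing it between arms understates any post-dose effect by an amount the documents do not let one quantify

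*SAP*

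**What the plan says.** Protocol 2.1.2 lists among the secondary endpoints "Peak viral load, time to peak viral load, rate of decline of viral load, and time to RSV RNA being undetectable". It does not say whether the peak must be a post-dose value.

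SAP 5.3.1.1, Table 1, settles that. The peak is the highest log10 "viral load at or after the baseline measurement", and the table adds of the selected record: "This can be the baseline record or an unscheduled record". SAP 5.2.1 makes the baseline a pre-dose value: "Baseline is defined as the last measurement before first intake". A swab up to one hour after treatment initiation can stand in only if there is no pre-treatment result. The inclusion of baseline is deliberate, because the companion time-to-peak rule provides for it: "Subjects for which the peak was reached at the baseline measurement will have time 0".

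SAP 5.3.2.1 uses the peak as a measure of treatment effect: "The log peak viral load and rate of decline of RSV RNA viral load will be compared for active groups versus placebo groups". The model for that comparison has two required terms, treatment and strata. Baseline viral load is not one of them. It is available only through the general covariate list in SAP 5.3.2, where it is the first entry and is chosen by stepwise selection. That list opens with the words "In the statistical models following predictive covariates and or baseline indicators may be included: baseline".

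**The concern.** The baseline swab precedes the loading dose, so treatment cannot change it. For any child whose maximum is that swab, the endpoint value is settled before exposure, and such children contribute nothing to the arm difference except noise. Entry is allowed up to 5 days after symptom onset (Protocol section 4), and SAP 1.4 assumes 40% of children enter within 3 days, hence 60% later. Some baseline peaks are therefore to be expected.

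The peak analysis also departs from the primary one. The model in SAP 5.2.3 takes only Days 2 to 7 as response and uses baseline as a covariate. The risk is one of interpretation: a small difference with its 95% interval could be read as little effect on peak shedding when the definition produced part of that result.

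**Working it through.** **1. The plan's own figure.** The documents give no power, effect size, SD or share peaking at baseline for this endpoint. The only power statement is for the primary AUC test, reproduced here to confirm the inputs used in step 4. From SAP 1.4:
- High-dose effect: 0.4 × 30% + 0.6 × 20% = 24% of placebo AUC.
- Low-dose effect: 0.8 × 24% = 19.2%.
- SD: 34% of placebo AUC; 60 per arm.
- Contrasts: plateau (−1, ½, ½) and linear (−1, 0, 1), with correlation 1.5 / (√1.5 × √2) = 0.866.

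The check used a constant Pocock boundary (z = 2.289, one-sided 0.0110 per look), looks assumed at 90, 120 and 180, and 10,000 simulations. Power is 96.4% at 180 (stated: about 97%) and 84% at the 120-subject look (stated: at least 80%).

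**2. A ceiling that needs no curve model.** Let B be baseline and P0, P1 the post-dose maxima on placebo and active. Randomization gives B the same mean in both arms, so

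E max(B, P0) − E max(B, P1) ≤ E max(B, P0) − E B = E max(P0 − B, 0).

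However good the drug, the difference cannot exceed placebo's mean rise above its own baseline. As an illustration, suppose every placebo child declines by 0.3-0.5 log10 per day, with six daily post-dose swabs and swab noise SD 0.7. The ceiling is then 0.24-0.39 log10. For noise SD from 0.3 to 1.0 it runs from 0.03 to 0.71. It is higher if many children are still rising at entry.

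**3. Simple dilution.** If a share f peaks at baseline, the effect shrinks to (1 − f)δ, and power = Φ[(1 − f)δ / √(2/n) − 1.96]. Take δ giving 80% power at n = 60: δ = (1.960 + 0.842) × √(2/60) = 0.511 SD. At f = 0.5: 0.5 × 0.511 / 0.1826 − 1.96 = −0.56, so power is 29%. Power is 71%, 50%, 13% and 5% at f = 0.1, 0.3, 0.7 and 0.9. At 40 per arm (the 120 expected in the ITT-i set under SAP 5.1.1), the 80% becomes 63%, and f = 0.5 gives 21%.

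**4. Simulated curves.** One active arm versus placebo, 60 per arm, two-sided 5%, one pre-dose and six daily post-dose swabs. The between-child spread was set to give an AUC SD of 34%, and the drug effect to give a 24% AUC reduction. Assumed, not from the documents: mean peak height 7.5 log10, rise 1.0 and fall 0.7 log10 per day, individual peak times with SD 1.2 days, mean peak time from −2 to +2 days around the first dose, and noise SD from 0.3 to 1.0. Selected rows, each pair given as SAP definition / post-dose maximum:

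| Mean peak day; noise SD | Peak at baseline (arms pooled) | Difference, log10 | Effect lost | Power %, unadjusted | Power %, baseline-adjusted |
|---|---|---|---|---|---|
| −2; 0.3 | 95% | 0.02 / 0.37 | 94% | 5 / 30 | 6 / 99 |
| 0; 0.7 | 57% | 0.27 / 0.59 | 54% | 12 / 40 | 52 / 76 |
| 0; 1.0 | 51% | 0.34 / 0.67 | 50% | 16 / 47 | 50 / 71 |
| +1; 0.3 | 36% | 0.52 / 0.70 | 25% | 31 / 49 | 97 / 96 |
| +2; 0.3 | 13% | 0.97 / 1.03 | 6% | 72 / 77 | 100 / 100 |

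Effect lost is taken from unrounded differences. The estimated difference shrinks in every row. With baseline adjustment, the power loss is large when most children peak at baseline, moderate at about half, and absent when few do.

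**The case against.** The strongest reply is that the definition is a reasonable description. For a child already declining at entry, the baseline value is the highest shedding observed, and the protocol does not limit the peak to post-dose values. A post-dose maximum will often be just the first post-dose swab, which overlaps with the Day 2 contrast from the primary model. Post-dose effects are also examined directly elsewhere: the Days 2-7 model, by-visit differences, decline over the first 24 hours, and AUC to Days 10 and 14. This stands as a limit on the harm. It does not explain why a partly pre-dose quantity should be compared between arms as a drug effect.

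A second reply is that the unadjusted power figures overstate the loss. Baseline viral load may enter by stepwise selection, SAP 5.3.2.1 refers to a final model for the peak, and baseline would be strongly correlated with a peak that includes it. This stands too: the adjusted figures are the more relevant ones. The covariate remains optional, and step 4 shows that it does not cure the definition.

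A reader might infer that about half the children have a peak fixed before treatment and that most of the effect and power is lost. The documents give no peak-timing data, so neither statement can be made. Even at one half, the loss is 50-54% of the effect, and a difference of 0.27-0.34 log10 remains.

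A reader might also infer that time to peak needs the same repair. It does not. That endpoint has only Kaplan-Meier summaries and no test between arms. With the next scheduled swab on Day 2, a post-dose restriction would only move the cluster from 0 hours to about 24 hours.

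**Conclusion.** The concern holds as a flaw in how one secondary endpoint is defined for comparison. The direction is certain: including the pre-dose swab attenuates the arm difference on peak viral load, and the attenuation grows with the share of children who peak at baseline. The size is unknown. Across the assumed curves, 13-95% peak at baseline and 6-94% of the effect is lost. At about half, power falls from 71-76% to 50-52% with baseline adjustment, and from 40-47% to 12-16% without it. These figures rest on 60 per arm, the assumed curve shapes, and the plan's 34% SD and 24% mean effect carried over from AUC. No power is claimed for the peak, and the primary dose-response test does not use it.

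**What to change.** For the between-arm comparison, define peak viral load as the highest log10 value from a swab taken after the first dose. Exclude any early post-dose swab that serves as baseline under SAP 5.2.1. Make baseline log10 viral load a fixed covariate in the SAP 5.3.2.1 peak model instead of leaving it to stepwise selection. Keep the baseline-inclusive peak as a descriptive row, and report by arm the number and percentage of children whose peak is the baseline record. Leave time to peak as it is.

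The cost is one derivation line in Table 1, one model term and one summary row, all from swabs already scheduled. The drawback is that the compared peak no longer describes the highest shedding observed in the child, which is why the descriptive row should stay.
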